Motor function for all animals will be tested between hours 7 and 9 of the light-phase. Beam traversal is performed first, before allowing animals to rest for ~1hr and testing on pole descent. The following day, adhesive removal and hind limb scoring will be performed. Fecal output will be performed within 3 days and immediately prior to tissue collection. **Beam traversal-** A 1 meter plexiglass beam (Stark's Plastics, Forest Park, OH) was constructed of four segments of 0.25m in length. Each segment is of thinner widths 3.5cm, 2.5cm, 1.5cm, and 0.5cm, with 1cm overhangs placed 1cm below the surface of the beam. The widest segment is a loading platform for the animals and the narrowest end placed into home cage. Animals will have two days of training to traverse the length of the beam before testing. On the third day, animals will be timed over three trials to traverse from the loading platform to the home cage. Timing will begin when the animals place their forelimbs onto the 2.5cm segment and end when one forelimb reaches the home cage. **Pole descent-** A 0.5m long pole, 1cm in diameter, is placed into the home cage. Animals receive two days of training to descend from the top of the pole and into the home cage. On the test day, animals are placed head-down on the top of the pole and timed to descend back into the home cage. Timing begins when the experimenter releases the animal and ends when one hind limb reached the home cage base. **Adhesive removal-** ¼" round adhesive labels (Avery, Glendale, CA) will be placed on the nasal bridge between the nostrils and forehead. Animals are placed into their home cage (with cage mates removed) and timed to completely remove the sticker. Animals are recorded over three trials. **Hind limb clasp reflex scoring-** Animals are gently lifted upwards by the mid-section of the tail and observed over ~5-10 seconds [80]. Animals are assigned a score of 0, 1, 2, 3 based on the extent to which the hind limbs clasped inward. 0, no clasping. A score of 1 is assigned to animals which clasp one hind limb inward or if both legs exhibit partial inward clasping. A score of 2 is given if both legs clasp inward for the majority of the observation, but still exhibit some flexibility. A score of 3 is assigned if animals display complete paralysis of hind limbs that immediately clasped inward and exhibited no signs of flexibility. **Inverted grid-** Animals are placed in the center of a 30cm by 30cm screen with 1cm wide mesh. The screen is inverted head-over-tail and placed on supports ~40cm above an open cage with deep bedding. Animals are timed until they release their grip or remain for 60s. All motor tests are video recorded, and a blinded investigator scores performance to validate scoring by unblinded investigators. **Fecal Output-** Animals are removed from their home cages and placed into a 12cm x 25cm translucent cylinder. Fecal pellets are counted every 5 minutes, cumulative over 15 minutes. Principal component analysis (PCoA) of all motor function and gut motility is performed using MATLAB software (MathWorks) using behavioral data collected from mice that performed at least 3 tasks. Data is centered and standardized ($\sigma = 1$) prior to running the PCoA function.

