
After testing, mice will be sacrificed and prepared for either histology or physiological recordings. For these particular studies, we will colonize 12 mice per condition and all will undergo behavioral evaluation. Within each condition and as described below, tissue from 4 mice will be evaluated for histology, 4 for population activity imaging, and 4 for whole cell patch clamp electrophysiology.

Histological evaluation of neuronal populations in cleared brain and GI tissue. Mice will be sacrificed via intracardial perfusion with 4% paraformaldehyde. To enable fine-scale neural circuit mapping in a whole unsectioned specimen by light microscopy, the opaque sample needs to be "cleared" to allow light penetration

throughout the whole sample. One effective tissue clearing technology, CLARITY, creates tissue-hydrogel hybrids that lock in place bio-macromolecules and are amenable to selective lipid extractions to increase optical

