Physiological recordings from brain and gut tissue. For recordings from the brain, thick slices (300 μ m) will be collected and incubated in oxygenated aCSF. Slices will then be mounted in a perfused chamber for recording. For recordings from GI tissue, 2 cm long segments of the GI tract will be cut and opened along the mesentery and incubated in oxygenated Krebs's solution with muscle relaxants (e.g. nicardipine, atropine). The tissue will then be microdissected to expose the myenteric or submucosal plexus and pinned to a perfused, Sylgard lined chamber, mucosa side up. We will perform whole cell patch clamp on both brain and GI tissue to assess passive (e.g. membrane resistance, resting potential), active (e.g. action potential threshold and amplitude), and synaptic (e.g. post synaptic currents) properties of neurons. In the brain, we will record from substantia nigra pars compacta. In the gut, we will record from both the myenteric and submucosal plexuses of the duodenum, jejunum, proximal colon, and distal colon. We will record a minimum of 12 neurons from each region in each mouse for comparison. By performing AAV-based labeling before microbiota transplantation as described above, specific cell types can easily be identified for recording. Separately, we will use AAVs to deliver a genetically encoded calcium indicator (e.g. GCaMP) for activity imaging. For the gut, tissue can be prepared without the need for microdissection and population dynamics can be recorded via fluorescent imaging in response to physiological stimuli (i.e. stretch, touch) [106].

Expected Outcomes for Specific Aim 2. We expect that ASO mice receiving transplants from PD donors will display increased pathology compared to mice with microbiota from HCs. Further, we predict animals receiving microbiota from low SCFA producers will display more severe motor deficits, while it may be difficult to resolve here which SCFAs mediate phenotypes (addressed in Aims 3 and 4). We expect to observe increased α Syn aggregation in both brain and gut tissue for animals with the worst motor defects. In the brain, we expect to see an increase in dopaminergic cell death or degeneration in mice transplanted with PD donor-derived microbiota, though phenotypes may be subtle such as deterioration of dopaminergic projections, primarily in the

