Fiber will be measured by the phenol sulfuric acid method and fibers adjusted to same fiber weights. Fecal samples provided by subjects will be, as quickly as possible, flash frozen in liquid nitrogen and thawed in the anaerobic chamber 30 minutes prior to analysis as per Rose et al. (2010) [112]. The bioreactor fermentation procedure will be similar to that described by Kaur et al. (2011) [99], except that all procedures will be done in an anaerobic chamber. Dietary fiber (1%) and 5% feces will be added to PBS buffer in an anaerobic tube, and sealed tubes incubated at 37 °C for 12 h, and in certain cases for a time course profile at various times from 0 to 24 h. Fermentation metabolites will be analyzed according to our protocol in Kaur et al. (2011) [99] by gas chromatography. Metagenomic analysis will be done as described in Aim 1.1. These studies will identify designer fibers that “normalize” SCFA ratios, or even improve upon SCFA ratios (i.e. elevate targeted SCFAs), in PD stool to that of healthy controls.

Aim 3.2. Normalizing SCFA ratios in a humanized mouse model of PD

Rationale. While bioreactors are useful due to high throughput capabilities, mouse models are needed to determine complex phenotypes. This sub-aim will test whether dietary management of the microbiome may be

a viable approach to modulate PD symptoms in humanized mice.

Experimental approach. We will generate independent mouse colonies harboring microbiota from 5 human PD patients, selected as those whose microbiomes and SCFA levels deviated the most from healthy controls, as

determined in Aim 1. 1. Both germ-free WT and ASO mice will be colonized. Beginning at 5-6 weeks of age, we will feed dietary fibers already known to increase ratios of the 3 major SCFAs continually in drinking water, and leave control groups unfed. Fiber doses will be determined empirically as the concentration in water required to achieve the desired output fiber concentrations in feces of GF mice (thus, accounting for background absorption and non-microbial breakdown). Starting at 12 weeks of age, mice will be motor tested, neuroinflammation determined and α Syn pathology assessed, as described in Aim 2. Microbiomes and metagenomes will be profiled, as described in Aim 1.1. SCFA levels will be tested in feces over time and colon contents upon sacrifice, to determine if metabolite profiles responded as predicted by the fiber administered.

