age, each animal group will be treated by oral gavage with 1) Lachnospiraceae; 2) Rikenellaceae; 3) Peptostreptococcaceae; or 4) mock gavage. Individual bacterial species will be chosen as those most phylogenetically similar to the OTUs from our data set and available from the American Type Culture Collection (ATCC; URL not provided as to adhere to DoD application guidelines). Bacteria will be grown in pure culture, and 1×10^9 colony forming units (CFU) will be administered to mice daily for 30 days; this regimen was chosen as it is a high dose and exposure, increasing likelihood for a positive result with future experiments aimed at optimizing treatment parameters. Fecal samples will be collected before and weekly during treatment for microbiome profiling. Following 30 days of treatment, mice will be tested for motor symptoms in beam traversal, pole descent, adhesive removal and hind limb claspings, as described in Specific aim 2, and shown in **Figure 3** and Sampson et al., 2016. For those microbial treatments that ameliorate motor deficits, mouse groups will be analyzed for neuroinflammation and α Syn aggregation as described in Aim 2. Finally, for those probiotic treatments that ameliorate motor symptoms, neuroinflammation and reduce α Syn aggregation, neuronal phenotyping and CLARITY will be performed comparing treated and untreated groups as described in Aim 2. This comprehensive analysis will not only identify novel microbial treatments for PD symptoms in mice, but is designed to reveal mechanisms of action for how beneficial bacteria may ameliorate the pathophysiologies that contribute to motor deficits.

In addition to the microbes to be tested from our existing data set, this project will generate new information that adds to the list of potentially therapeutic microbes based on a larger cohort size, as described in Aim 1. Depending on the number of new bacterial candidates, mice can be treated first with pools of species and then narrowed down, or treated with single species from the onset. Description of experimental approaches similar to the studies above. This research will identify additional microbes with therapeutic potential.

Aim 4.2. Combine prebiotic and probiotic treatments to optimize disease protection in mice

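### Unblinded investigators score the mouse motor tests and the blinded video score only checks them, leaving avoidable observer bias in Aims 2, 3.2, 4.1 and 4.2

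*Protocol*

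**What the plan says.** The rule on who scores stands in the Protocol under Specific aim 2, Experimental Approach (behavioural analysis of colonized mice): "All motor tests are video recorded, and a blinded investigator scores performance to validate scoring by unblinded investigators". No other use of the blinded scores appears in the Protocol. The same section feeds the behavioural data into a principal component analysis without saying whose scores are used, and the Statistical analysis paragraph does not mention blinding.

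Among the tests, the clasp reflex is graded by eye: "Animals are assigned a score of 0, 1, 2, 3 based on the extent to which the hind limbs clasped inward". Beam, pole, adhesive and inverted grid are timed to defined end events.

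On size and scope:

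- Aim 2: "we will colonize 12 mice per condition and all will undergo behavioral evaluation".
- Aim 3.2: "Starting at 12 weeks of age, mice will be motor tested, neuroinflammation determined and" so on, by the Aim 2 methods.
- Aim 4.1: "mice will be tested for motor symptoms in beam traversal, pole descent, adhesive removal and hind limb claspings, as described in Specific aim 2".
- Aim 4.2 relies on motor methods already described.

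Aim 4.1 then uses the motor result as a filter: "For those microbial treatments that ameliorate motor deficits, mouse groups will be analyzed for neuroinflammation" and αSyn aggregation. The step after that, neuronal phenotyping and CLARITY, is for treatments with benefit on all of these: "Finally, for those probiotic treatments that ameliorate motor symptoms, neuroinflammation and reduce" αSyn aggregation.

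**The concern.** A person who knows genotype, donor and treatment produces the score, and the expected direction is on record. Expected Outcomes for Specific Aim 2 says: "Further, we predict animals receiving microbiota from low SCFA producers will display more severe motor deficits". The same paragraph expects more pathology with PD donors.

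The blinded reading could reveal a drift if it were compared by group. Nothing says that it must be, what difference would count, or that the blinded score would then replace the unblinded one. A check with no consequence does not protect the analysed data.

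At stake are the donor contrast in Aim 2, which could be exaggerated, and the first filter in Aim 4.1, which could pass an ineffective treatment.

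**Working it through.** There is no figure in the plan to reproduce; the finding rests on the wording. The arithmetic below only shows what a given scoring shift would do.

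**Inputs from the Protocol.** 12 mice per condition (Aim 2). 6-8 mice per group in general, two-sided 5% level (Statistical analysis).

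**Assumed inputs.** No true effect. One group's scores are shifted by d = 0.2, 0.3 or 0.5 SD, and the validation step does not correct it. Two groups, one run, unadjusted t-test.

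**Step 1: false-positive rate.** With n per group, the t statistic follows a noncentral t with 2n − 2 degrees of freedom and noncentrality d√(n/2). The rate is the probability that it falls outside ± the 97.5% point of the central t.

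| n per group | df | √(n/2) | Noncentrality at d = 0.2 / 0.3 / 0.5 | Rate at d = 0.2 / 0.3 / 0.5 |
|---|---|---|---|---|
| 6 | 10 | 1.732 | 0.35 / 0.52 / 0.87 | 6.1% / 7.6% / 12.3% |
| 8 | 14 | 2.000 | 0.40 / 0.60 / 1.00 | 6.6% / 8.7% / 15.4% |
| 12 | 22 | 2.449 | 0.49 / 0.73 / 1.22 | 7.6% / 10.8% / 21.6% |

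At d = 0 every row returns 5.0%. Pooling two runs of 8 (16 per group) gives 8.5% / 13.0% / 27.8%. A systematic shift does more damage as numbers grow, so pooling duplicate runs is no protection if both are scored the same way.

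**Step 2: what such a shift means on the clasp score.** Suppose each animal in one group scoring below 3 is raised one grade with probability p. The mean rises by p × (proportion below 3). Dividing by the SD gives the shift. The Protocol gives no score distribution, so three are assumed.

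| Assumed share at 0/1/2/3 | SD | p = 1/4 | p = 1/2 |
|---|---|---|---|
| 25/25/25/25% | 1.118 | 0.25 × 0.75 / 1.118 = 0.17 | 0.34 |
| 30/40/20/10% | 0.943 | 0.25 × 0.90 / 0.943 = 0.24 | 0.48 |
| 10/40/40/10% | 0.806 | 0.25 × 0.90 / 0.806 = 0.28 | 0.56 |

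On these assumptions, shifts of 0.2-0.3 SD need roughly one animal in four graded one step too high, and 0.5 SD roughly one in two.

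**The case against.** The strongest reply is that a blinded check exists and that the Protocol nowhere says the unblinded score prevails; the word only is a reading. Agreement limits and the choice of analysed score are also often left to an analysis plan or a laboratory procedure. This has some force, and a later document could add such a rule. But the Protocol itself allots the roles: what is validated is the unblinded score, and the blinded score has no other stated use. The point is that stated hierarchy, not merely a missing detail.

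Second, the shift sizes are assumed and taken to go uncorrected. At 6-8 mice, shifts of 0.2-0.3 SD give 6.1-8.7%, an excess of 1.1 to 3.7 points over 5%. That stands: the calculation illustrates and does not measure.

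Third, the planned analysis is ANOVA with Holm-Sidak comparisons, in duplicate, not a single t-test. The rates are therefore not the design's own error rates. If both of two independent runs had to be positive, which the Protocol does not say, 8.7% would become 0.087² = 0.8%. The unbiased figure would then be 0.05² = 0.25%, so the inflation would remain, at about threefold.

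Fourth, clasping is one of four tests listed in Aim 4.1, the other three are timed, and a false pass leads first to further assays, with CLARITY behind a stricter filter. That limits the harm to the first step. It does not remove it, since the Protocol does not say how the four tests combine into a pass.

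Fifth, blinded scoring leaves unblinded handling in place; pole timing, for example, starts when the experimenter lets go. That is true and is a limit of the remedy.

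**Conclusion.** The concern holds. The Protocol gives the unblinded scorer the primary role and the blinded scorer a supporting one, for outcomes that run through four mouse sub-studies and act as a filter in one of them. The weakness is real but partial: a blinded reading is planned, the clasp score is the main exposure, and the human work in Aim 1 is untouched.

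Its size cannot be derived from the documents. If shifts of 0.2-0.5 SD went uncorrected, a nominal 5% test would run at about 6-12% with 6 mice per group, 7-15% with 8 and 8-22% with 12. The change should be made because the bias is avoidable with resources already planned, not because a particular error rate has been shown.

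**What to change.** Replace the scoring sentence in Specific aim 2 with wording to this effect:

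*Every motor test is filmed. The analysed data, including those behind the Aim 4.1 decision, are the video scores of an investigator blinded to genotype, donor and treatment. Live unblinded scores are used only where a video is unusable, and to report agreement by group.*

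Aims 3.2, 4.1 and 4.2 refer back to this text, so one edit covers them. The cost is low, because filming and a blinded scorer are already planned. The Protocol does not say that every video is read blind, so there would be extra scoring time if only a subset was intended. Bias from unblinded placement and release of the animals would remain.

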Aim 1.2. Identify the potential contributing factors for dysbiosis in PD

Rationale. It is well established that environmental factors such as diet, as well as genetics, impact microbiome composition [93]. Currently, there are no data for how environment impacts the microbiome in PD. Filling this knowledge gap can advance our understanding of the underlying mechanism of dysbiosis in PD and provide an opportunity for disease modification in those at high risk of developing PD, such as first-degree relatives.

Experimental Approach. In order to determine the contribution of environmental and genetic factors to dysbiosis in PD, we propose two approaches. First, a cross sectional study where we will compare microbiome composition in subsets of PD patients (newly recruited as part of the proposed application) whose household, non-related spouse (for environmental factor) and their first-degree relatives who do not live with the patient agree to provide stool samples as well. The consent process will be initiated after the subject has been initially screened for eligibility. If the patient meets inclusion and exclusion criteria, the subject will be approached by a member of the study staff during his/her regular clinic visit or sent a copy of the consent form so that they may read it in the comfort of their own home. If the potential subjects' spouse/ relative accompany during the clinic visit, they will be informed about the study. If not, the subject will be asked to share the study information with their spouse/ relative and inform the study team if interested. If the subject is interested in moving forward, the consent will be reviewed by the study coordinator in the Gastroenterology clinic. The study coordinator, PI or study staff delegated the responsibility by the PI will obtain informed consent from the subject.

We also plan to have the study registered on clinicaltrials.gov and the Michael J Fox trial finder so that interested participants can contact the study team.

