Each household and first-degree relative study subject will be evaluated to ensure there is no clinical evidence of neurological disorders including PD. Also, these subjects will complete a 24 hour diet recall questionnaire before stool collection and validated 3 month food frequency questionnaires to collect dietary information similar to PD patients. Each subject (including PD subjects) will complete a smell questionnaire and a sleep questionnaire to determine whether these “control” subjects have loss of smell or have REM sleep disorders because these

conditions increase the risk of PD. For assessing smell, we will use the UPSIT questionnaire [94, 95]. For assessing REM sleep disorder, we will use RBD1Q which consists of a single question, answered “yes” or “no,” as follows: “Have you ever been told, or suspected yourself, that you seem to ‘act out your dreams’ while asleep (for example, punching, flailing your arms in the air, making running movements, etc.)?” [96] We predict that at least 20 PD patients/MSA will have both household spouse and first degree relative willing to provide stool samples for this study.

Second, in the longitudinal study, we will collect stool every 3 months (with 3 day diet questionnaire prior to each collection) over 12 months and determine microbiome composition over time. All PD subjects will undergo clinical assessments at baseline and end of the study to determine the severity of PD. These assessments will include: Movement Disorder Society-Sponsored Revision of the Unified Parkinson’s Disease Rating Scale (MDS-UPDRS); Hoehn and Yahr Stage (HY); Non-Motor symptoms Scale (NMSS); Montreal Cognitive Assessment (MoCA). We will correlate the microbiome data with PD symptoms, diet and response to treatment and progression of disease. These studies will determine whether disease progression and factors such as PD medications and diet significantly impact microbiome composition. Further, we will determine whether changes in SCFA-producing bacteria (as part of Aim 1.1) and/or abnormal SCFA profiles (as part of Aim 1.3) correlate with severity of PD symptoms.

Inclusion/ Exclusion Criteria:

For Parkinson’s disease subjects:

Inclusion criteria:

1. 40-80 years of age
2. Documented diagnosis of Parkinson’s disease
 - For cross sectional study- the Parkinson’s disease stages 1-4 are eligible
 - For longitudinal study- the Parkinson’s disease stages 1-2.5 are eligible

Exclusion criteria:

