Statistical analysis. Group descriptive statistics will be performed on all variables. Normality of distribution will be assessed by the Lilliefors test, and homogeneity of variance will be examined with the Levene test. Inter-group differences will be analyzed by one or two-way ANOVA using the Holm-Sidak test for comparison. For animal research, based on our previous studies over many years, 6-8 mice per group will be needed (and all studies performed in duplicate) on average in each group to achieve a probability of 88% that the study will detect a relationship between independent and dependent variables at a two-sided 5% significance level. This power calculation assumes that the true change in the dependent variables is 0.53 standard deviations per one standard deviation change in the independent variable. For human subjects work, based on the humanized mouse data in **Figure 4** and our publication [30], a sample size of 20 human donors per group achieves 96% power to detect a small effect size ($f^2 = 0.08$) attributed by patient category by an F-test with an $\alpha = 0.05$, when adjusting for 7 additional explanatory variables.

Overall Strategic Plan. De-identified stool samples collected at RUMC will be sent to Caltech for colonization of mice, as we have been doing for over 2 years. Additional samples for ongoing enrollment will be collected at RUMC and UW. Fecal swabs from all samples will be sent to UCSD for microbiome profiling (metagenomics). All samples will be coded so that investigators at Rush and UW can link it back to the subjects. Investigators from UCSD, Caltech and Purdue will not have access to the link to the codes with subject identifiers. Fibers will be developed and optimized in bioreactors at Purdue. Fecal samples and dietary fibers will be sent to Caltech, where all mouse treatments will take place. Fecal samples from Rush will also be sent to the [name] lab at Purdue to perform *in vitro* fermentation tests. The [name] laboratory will administer the motor tests, assess neuroinflammation, and measure α Syn aggregation; while the [name] laboratory will perform the CLARITY analysis and neuronal activity tests. Finally, fecal samples from mice will be sent to UCSD for metagenomics, and to Purdue for *in vitro* fermentation and SCFA analysis. We predict that specific, molecular interactions

Formatted: Font: Italic

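### The protocol names plain one- or two-way ANOVA for group differences but sizes the human groups on a covariate-adjusted F-test; followed as written, the ANOVA risks confounding in patient-control comparisons and wastes the family design

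*Protocol*

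**What the plan says.** Protocol, Statistical analysis: "Inter-group differences will be analyzed by one or two-way ANOVA using the Holm-Sidak test for comparison". No covariate, family or subject term accompanies this sentence. It stands before both the animal and the human sample-size statements and is not limited to either.

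The same paragraph then states, for the human work, that "a sample size of 20 human donors per group achieves 96% power to detect a small effect size" (f² = 0.08) in an F-test for patient category at alpha 0.05, "when adjusting for 7 additional explanatory variables". The 7 variables are not named.

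Aim 1.2, Experimental Approach, plans "a cross sectional study where we will compare microbiome composition in subsets of PD patients", each with a household, "non-related spouse (for environmental factor) and their first-degree relatives who do not live with the patient". The protocol predicts at least 20 index patients who "will have both household spouse and first degree relative willing to provide stool samples for this study".

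Aim 1.1 says the healthy controls are matched on age, gender, race and BMI. Diet is not in that list, and no matching is stated for the two other synucleinopathy groups. The background section on diet and PD concludes that patients appear to eat less fiber than controls.

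**The concern.** The test named for group differences is not the test that was powered. If the ANOVA sentence is followed for human data, two different things go wrong.

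- **Patients versus unrelated controls.** A factor such as diet, which the protocol expects to differ between groups and to shape the microbiome, stays inside the category effect. A significant result could then reflect fiber intake rather than disease, and more subjects do not cure that.
- **Trios.** Spouse and relative are sampled because they are linked to the patient. A one-way ANOVA treats the three members as strangers and discards the information that the linkage was meant to provide on environmental versus genetic contributions.

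**Working it through.** **Can the named test be the powered test?** A two-way ANOVA has two factors. Category plus 7 further variables makes eight terms, and category, family and 7 covariates make nine. Neither fits.

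**The plan's own power figure.** Inputs from the Statistical analysis paragraph: f² = 0.08, alpha 0.05, 7 covariates, 20 per group. With g groups, N = 20g, u = g − 1, v = N − u − 7 − 1 and noncentrality λ = f²N.

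| Groups | N | u, v | λ | Power |
|---|---|---|---|---|
| 2 | 40 | 1, 31 | 3.2 | 41% |
| 3 | 60 | 2, 50 | 4.8 | 46% |
| 4 | 80 | 3, 69 | 6.4 | 52% |
| 5 | 100 | 4, 88 | 8.0 | 58% |

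The stated 96% is not reached. It would need about 175 subjects with two groups (88 per group) or 207 with three (69 per group). The covariates are not the cause: without them, power at N = 40 is 41.4% instead of 41.1%.

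**Confounding in patient-control comparisons.** Assumptions: category has no effect at equal covariate value; the covariate differs by d SD between groups; it correlates r with the outcome within group. The unadjusted t (or F) test then has noncentrality δ = r·d / √(1/n₁ + 1/n₂).

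- 20 versus 20, √0.1 = 0.316: d = 0.5, r = 0.2 gives δ = 0.10/0.316 = 0.32 and type I error 6%; d = 1.0, r = 0.5 gives δ = 0.50/0.316 = 1.58 and 34%.
- 40 versus 20 (the biobank numbers in Aim 1.1), √0.075 = 0.274: the same corners give δ = 0.37 and 1.83, and type I error of about 7% and 43%.
- Adjusting for the covariate returns the error to about 5%.

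**Power lost even if covariates are balanced.** If they explain a share R² of within-category variance (assumed 10% to 40%), the unadjusted effect is 0.08(1 − R²). Power falls from 41% to between 38% and 27% at N = 40, and from 46% to between 42% and 30% at N = 60.

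**Trios.** Assume 20 trios, unit variance and equal within-family correlation ρ. The true variance of a patient-minus-spouse mean difference is 2(1 − ρ)/20; the one-way ANOVA uses 2/20. It overstates that variance by 1/(1 − ρ): 1.25-fold at ρ = 0.2 and 2-fold at ρ = 0.5. Simulation with at least 20,000 data sets per cell gives:

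| ρ | Null rejection, one-way / family block | Power at 0.5 SD patient shift, one-way / family block |
|---|---|---|
| 0.2 | 2.5% / 5% | 30–31% / 40% |
| 0.3 | 1.6% / 5% | 28–29% / 45–46% |
| 0.5 | 0.4% / 5% | 23–24% / 59–60% |

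**Unequal family correlations.** If spouse and relative are uncorrelated and each correlates 0.5 with the patient, the blocked omnibus F-test rejects about 6% under the null. The paired patient-spouse contrast stays at about 5% throughout. Its power at 0.5 SD, before multiplicity correction, is about 39% to 57%, against 28% to 32% unpaired.

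**The case against.** The ANOVA sentence is generic. It can be read as the mouse method, with the adjusted F-test as the human model. A two-way layout could also hold category and family. Covariate lists and random effects are usually settled in a statistical analysis plan, which is not at hand. Finally, microbiome composition is multivariate, other methods such as ordination and correlation are described, and nothing assigns a one-way ANOVA to the trios by name.

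Much of this stands. That the covariates are unnamed, or that a family term is absent, is no finding by itself. The benign readings are possible, but the protocol does not state them, and the ANOVA sentence as worded covers all inter-group differences. What remains is a method fixed in one sentence and a different one powered a few lines later.

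Two further readings are tempting and should not be adopted:

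- A reader might infer that lost power is the main cost everywhere. That is right for the trios. For patient-control contrasts it would require covariates unrelated to category, which the protocol's own statement on fiber intake contradicts.
- A reader might infer that serial stools will be analyzed as independent. Aim 1.2 says that "in the longitudinal study, we will collect stool every 3 months (with 3 day diet questionnaire prior to each collection) over 12 months" and that "We will correlate the microbiome data with PD symptoms, diet and response to treatment and progression of disease". It does not say that samples are pooled, so no error rate can be charged to the plan.

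**Conclusion.** The concern holds as an inconsistency inside the Statistical analysis paragraph that should be fixed, with different consequences for two sets of comparisons. For patients versus controls, the unadjusted ANOVA risks confounding (type I error about 6% to 34% at 20 versus 20) and also loses some power. For the trios it is conservative and costs roughly 10 to 36 percentage points of power at a 0.5 SD shift.

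The covariate gaps, correlations, R² values and shifts are assumptions; the protocol gives none of them. The contradiction itself does not depend on them. The sizes apply only if the ANOVA sentence is followed for human data.

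The 96% power figure is a separate error in the same paragraph. Adjusting for covariates does not repair it.

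**What to change.** 1. State that human patient-category comparisons use a linear model adjusted for the same covariates that the power statement assumes, named in advance and including diet. Keep plain ANOVA with Holm-Sidak for the mouse work.
2. For the Aim 1.2 trios, make paired patient-spouse and patient-relative contrasts under Holm-Sidak the main analysis. A family-blocked omnibus test can support them but should not lead, given its error of about 6% when family correlations differ.
3. Restate the human power for the chosen model and the actual number of groups.

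The cost is wording, minor programming and a few degrees of freedom. The one practical demand is that the chosen covariates be recorded in every human group, so they should be settled while collection is still open.
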